15.3 Appendix C. Additional Definitions of Adverse Risk AML

As detailed in protocol inclusion criteria #4, patients are eligible if they have adverse-risk disease including adverse karyotype. Adverse karyotype, as determined by cytogenetic evaluation, includes the following:

inv(3)(q21q26)/ t(3;3)(q21;q26)
t(3;21)(q26.2;q22.1)*
t(1;3)(p36.3;q21.1)
t(3;5)(q25;q34)*
-5*/ del(5q)*/ add(5q)
-7*/ del(7q)*/ add(7q)
t(11q23)
including: t(11;16)(q23;p13.3)*/ t(2;11)(p21;q23)*
t(8;16)(p11;13)
t(6;9)(p23;q34)
abnormal 17p (translocation or del*)
including: i(17q)*
-17
complex karyotype [≥ 3 unrelated abnormalities]*

* indicates that a karyotype may also be considered an MDS-related abnormality.

In the event that a karyotype (not listed above) is identified which the Investigator believes is associated with a high risk of AML relapse and no other criteria are present (i.e., antecedent hematologic disorder, presence of MRD), consideration for inclusion may be discussed with the Medical Monitor and documentation of the relapse risk included in the patient's study/medical record.

Other AML-related mutations and fusion genes/re-arrangements that are considered adverse-risk, with or without a concomitant karyotypic abnormality, include the following:

Mutations:

FLT3-ITD [internal tandem duplication]
MLL including MLL-PTD [partial tandem duplication]
TP53

Fusion genes:

MLL re-arrangements including MLL-CBP
RUNX1-RPL22L1, RUNX1-MDS1-EVI1.

15.4 Appendix D. Minimal Residual Disease (MRD) Definitions

MRD in the bone marrow of patients with AML in remission may be detected by one or more of the following laboratory methodologies:

1. Multi-parametric flow cytometry for detection of LAIPs. LAIPs include asynchronous expression of antigens (i.e., aberrant expression of antigens across maturation stages, such as coexpression of early and late antigens), cross-lineage expression of lymphoid markers, and overexpression or absence of lineage-appropriate markers. (Several populations with different LAIPs may be identified within a single patient/case).
2. Cytogenetic or FISH assessment for chromosomal translocations and deletions (partial or entire), including those detailed in the prior section/appendix as defining high-risk AML, and chromosomal abnormalities associated with favorable or intermediate-risk AML that persist following induction therapy and hematologic CR/CRI. These intermediate/favorable-risk abnormalities include:

t(9,11)(p21;q23)
-Y
+8 (trisomy 8)
t(8,21)(q22;q22)
inv(16)(p13.1q22)/ t(16;16;)(p13.1;q22).

(Although the core binding factor leukemias [CBF-AML, involving the t(8,21) and inv(16) abnormalities] have historically been associated with relatively good prognosis, relatively recent data suggest that patients with CBF-AML and concomitant FLT-ITD mutations and/or evidence of MRD following induction therapy may be at significant risk for relapse, with post-CR relapse risk approaching or exceeding 50%).

3. Real-time PCR based assessment of gene mutations including those detailed in the prior section/appendix as defining high-risk AML, and mutations associated with favorable/intermediate-risk AML that persist following induction therapy and hematologic CR/CRI. These favorable/intermediate-risk abnormalities include: RUNX1T1-RUNX1, CBFB-MYH11, MLLT3-MLL, RBM15-MKL1, MLL-ELL, MLL-MLLT1.
4. Next generation sequencing for the persistence of somatic mutations in the coding sequence of AML-associated genes, including the MDACC-based 28-gene AML panel (which includes gene mutations considered definitive of high-risk AML, and other AML associated mutations including: IDH1, IDH2, DNMT3A, ASXL1, TET2, N-RAS, K-RAS and others) and the Dana Farber Cancer Institute 95-gene sequencing panel.

15.5 Appendix E. CLS Management Guidance

CLS Element	Time of Presentation	Recommended Action	SL-401 Dosing Management
Serum albumin <3.2 g/dL (without albumin supplementation)	Prior to 1 st SL-401 administration	Do not dose (patient not eligible for participation)	
Serum albumin <3.5 g/dL OR reduced by ≥0.5 g/dL from pre-dose value (with or without albumin supplementation) A pre-dose body weight that is increased by ≥1.5 kg over the previous day's pre-dose weight	During SL-401 dosing ¹	
 • For the CLS element of albumin decrease: 
 ▪ Administer albumin 25 g IV (q12h or more frequently as practical) until serum albumin is both ≥3.5 g/dL and not reduced by ≥0.5 g/dL from pre-dose value • For the CLS element of body weight increase: 
 ▪ Administer albumin 25 g IV (q12h or more frequently as practical), and manage fluids and blood pressure, as clinically indicated, until body weight increase has resolved (i.e. the increase is no longer greater than 1.5 kg from the previous day's pre-dose weight) 	
 • Hold SL-401 dosing until the relevant CLS element has resolved as specified by Recommended action²
Edema, fluid overload and/or hypotension		
 • Administer albumin 25 g IV (q12h, or more frequently as practical) until serum albumin is ≥3.5 g/dL • Administer 1 mg/kg of methylprednisolone (or an equivalent) per day, until resolution of CLS element or as clinically indicated • Aggressive management of fluids status, which could include intravenous fluids and/or diuretics, until resolution of CLS element or as clinically indicated 	

1. For patients eligible for treatment with SL-401 with serum albumin >3.2 g/dL but <3.5 g/dL on the day of dosing, IV albumin (25 g) is recommended prior to administration of SL-401 to increase the serum albumin to ≥3.5 g/dL before the 1st dose of SL-401.
2. SL-401 administration may resume in the same cycle if all CLS elements have resolved and the patient did not require measures to treat hemodynamic instability. SL-401 administration should be held for the remainder of the cycle if CLS elements have not resolved or the patient required measures to treat hemodynamic instability (even if resolved), and SL-401 administration may only resume in the next cycle if all CLS elements have resolved, and the patient is hemodynamically stable.

CTCAE	Common Terminology Criteria for Adverse Events
DLT	Dose-limiting toxicity
DT	Diphtheria toxin
ECOG	Eastern Cooperative Oncology Group
ECG	Electrocardiogram
eCRF	Electronic case report form
IL-3	Interleukin-3
IL-3R	Interleukin-3 receptor
MedDRA	Medical Dictionary for Regulatory Activities
mITT	Modified Intent-to-Treat
MRD	Minimal residual disease
MTD	Maximum tolerated dose
OS	Overall survival
PCS	Potentially clinically significant
PK	Pharmacokinetic
PT	Preferred Term
RFS	Relapse-free survival
SAE	Serious adverse event
SAP	Statistical analysis plan
SCT	Stem cell transplant
SD	Standard deviation
SMQ	Standardized medical queries
SOC	System organ class

Abbreviation	Definition
TEAE	Treatment-emergent adverse event
ULN	Upper limit of normal
WHO	World Health Organization

1. INFORMATION FROM THE STUDY PROTOCOL

1.1. Introduction and Objectives

The overall purpose of study STML-401-0214 is to support the development of SL-401 and assess safety and clinical efficacy of the product in treatment of patients with acute myeloid leukemia (AML).

AML is characterized by the uncontrolled proliferation of immature myeloid cells in the bone marrow and peripheral blood, resulting in the development of anemia, neutropenia, and thrombocytopenia, and associated complications such as serious infections, bleeding, and fatigue. The median age at diagnosis is 67 years, and 5-year survival across all ages, treatments, and other prognostic groups is 24% ([National Cancer Institute 2013](#)). For AML patients who achieve hematologic remission following induction therapy, the evaluation of Minimal Residual Disease (MRD) provides additional information concerning the risk of relapse and mortality. The identification of MRD following AML remission has been associated with higher rates of relapse and diminished survival; for patients with intermediate risk AML in remission after 2 cycles of induction therapy, 1-year relapse rates were >60% for those with evidence of MRD versus <30% for those without MRD ([Terwijn et al 2013](#)). Approximately 70% of patients who receive first-line therapy and achieve a first complete response to treatment are expected to experience recurrent disease, and a subset of those who do not derive benefit from first-line treatment are candidates for subsequent therapy.

Although Complete Response (CR) rates after standard first-line induction therapy in AML are high, some subgroups of AML patients have limited tolerability of those regimens or have a high risk of relapse, even following the administered therapies (e.g. MRD). As a result, the National Comprehensive Cancer Network Guidelines (2013) recommend that AML patients with antecedent hematologic disease, age >60, or unfavorable cytogenetics are appropriate candidates for clinical studies with novel agents, even early in their disease. In addition, as there are no approved second-line AML treatments, there is unmet medical need for the relapsed/refractory population.

The target population for this clinical study is adult patients with adverse risk AML in first CR and/or with evidence of MRD in first CR.

1.1.1. Tagraxafusp (SL-401)

Diphtheria toxin (DT) Interleukin-3 (IL-3) fusion protein, named Tagraxofusp following Biologics Licensing Application (designated SL-401 during clinical development by Stemline Therapeutics, Inc. [“Stemline”]) is a novel biologic targeted therapy directed to the IL-3 receptor (IL-3R), a biomarker that is over-expressed on AML blasts and cancer stem cells (CSCs) relative to normal hematopoietic stem cells ([Jordan, et al. 2006](#); [Jordan, et al. 2000](#); [Tehranchi, et al. 2010](#)). Tagraxofusp is comprised of recombinant human IL-3 genetically fused to a truncated DT in which the binding domain of DT has been replaced with IL-3. The IL-3 domain of Tagraxofusp is able to target the agent to leukemia blasts and CSCs that over-express IL-3R, leading to receptor-mediated endocytosis and localization of Tagraxofusp to early endosomes. This allows Tagraxofusp to kill cells in a distinct manner from other cancer therapeutics. First, Tagraxofusp is a targeted therapy directed to the IL-3R that is present on CSCs and tumor bulk, but not on normal hematopoietic stem cells. Second, Tagraxofusp utilizes

a payload that is not cell cycle-dependent. Therefore, it is designed to kill not just highly proliferative tumor bulk, but also relatively quiescent CSCs. Lastly, Tagraxofusp utilizes a payload that may not be subject to multi-drug resistance mechanisms typically used by CSCs to evade traditional therapies. The payload also kills cells in a manner that is distinct from that of other available therapies, which is another reason why Tagraxofusp may be an effective addition to the therapeutic armamentarium against certain hematologic malignancies.

This study, STML-401-0214, was designed as a non-randomized, open-label, dose escalation, multicenter study, divided into 2 stages. Stage 1 (dose escalation) enrolled 9-18 patients with AML. Stage 2 (expansion) enrolled up to 20 additional patients with evidence of MRD.

1.1.2. Study Objectives

The following objectives are as defined in the Study Protocol (Amendment 5, 27 March 2018).

The primary objectives are to determine the maximum tolerated dose (MTD), or the maximum tested dose where multiple dose-limiting toxicities (DLTs) are not observed, of Tagraxofusp, and to characterize the safety profile of Tagraxofusp at the MTD or maximum tested dose.

Secondary objectives include:

- Evaluate the presence of MRD and changes in MRD status during and following Tagraxofusp therapy
- Estimate relapsed-free survival (RFS)
- Estimate overall survival (OS)
- Characterize the pharmacokinetics (PK) of Tagraxofusp
- Characterize the immunogenicity of Tagraxofusp.

Exploratory objectives are to characterize expression of IL-3R/CD123 (and other potentially relevant stem cell and disease markers) on leukemia cells in bone marrow (when feasible), to evaluate potential changes in IL-3R/CD123 (and other potentially relevant markers) expressing populations over time, and preliminary correlation of baseline IL-3R/CD123 (and other potentially relevant markers) expression and clinical efficacy (including changes in MRD status).

1.1.3. Purpose of this Document

This statistical analysis plan (SAP) is designed to outline the methods to be used in the analysis of study data in order to answer the study objective(s). Populations for analysis, data handling rules, statistical methods, and formats for data presentation are provided. The statistical analyses and summary tabulations described in this SAP will provide the basis for the results sections of the clinical study report (CSR) for this trial.

This SAP will also outline any differences in the currently planned analytical objectives relative to those planned in the study protocol.

1.2. Study Design

1.2.1. Synopsis of Study Design

This study is a non-randomized, open-label, dose escalation, multicenter study, divided into 2 stages: Stage 1, dose escalation and Stage 2, expansion. A cycle of therapy is 28 days.

Stage 1 (dose escalation) was designed to identify a MTD. During Stage 1, approximately 9-18 patients were planned to be treated with Tagraxofusp. The starting dose of Tagraxofusp was 7 µg/kg/day for 5 consecutive days every 28 days, with escalation to 9 and 12 µg/kg/day. Three to 6 patients were planned to be treated at each dose level. All enrolled subjects at each corresponding dose were enrolled and followed for their complete first cycle before additional patients could be enrolled. If 0/3 patients experienced a DLT, 3 new patients would be enrolled at the next sequential dose level. If 1/3 patients experienced a DLT, 3 additional patients would be enrolled at the same dose level. If 1/6 patients experienced a DLT, dose escalation could continue with dosing of a new cohort at the next higher dose level. If 2/3 or 2/6 patients experienced a DLT, the MTD was exceeded and further dose escalation would not occur. The MTD was defined as the dose preceding the dose level at which 2 or more patients experience a DLT during treatment Cycle 1. No intra-patient dose escalation was allowed.

During Stage 1, DLT was defined as any of the following occurring during the first cycle of therapy:

- Any treatment-emergent Grade 4 transaminase or creatine phosphokinase (CPK) elevation (confirmed within 24 hours of initial identification), regardless of duration or relationship to Tagraxofusp.
- Any treatment-emergent Grade 4 hematologic toxicity (unrelated to recurrent leukemia or prior AML therapy) lasting > 28 days after last infusion of Tagraxofusp.
- Any treatment-emergent Grade ≥ 3 non-hematologic toxicity (unrelated to recurrent leukemia), with the exception of Grade 3 laboratory toxicities that resolve to Grade ≤ 1 or baseline ≤ 28 days after the last infusion of Tagraxofusp, or the following Grade 3 toxicities if they resolve to Grade ≤ 1 or baseline ≤ 28 days after last infusion of Tagraxofusp: arthralgia, myalgia, fever responding to treatment, nausea and/or vomiting (excluding cases that require tube feeding, total parenteral nutrition or hospitalization) or diarrhea associated with suboptimal prophylaxis or treatment.

During Stage 2 (expansion), up to 20 additional patients with evidence of MRD as determined locally would be treated at the MTD or maximum tested dose at which multiple DLTs are not observed (identified as 12 µg/kg/day in Stage 1) so that up to 15 patients with evidence of MRD as determined centrally would be evaluable for safety and response at this dose.

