- Any treatment-emergent Grade ≥ 3 non-hematologic toxicity (unrelated to recurrent leukemia), with the exception of Grade 3 laboratory toxicities that resolve to Grade ≤ 1 or baseline ≤ 28 days after the last infusion of SL-401, or the following Grade 3 toxicities if they resolve to Grade ≤ 1 or baseline ≤ 21 days after the last infusion of SL-401: arthralgia, myalgia, fever responding to treatment, nausea and/or vomiting (excluding cases that require tube feeding, total parenteral nutrition, or hospitalization) or diarrhea associated with suboptimal prophylaxis or treatment.

SL-401-related toxicities are AEs that are considered by the Investigator to be either possibly, probably or

definitely related to investigational SL-401 (Please refer to Section 10.6 for more thorough guidance as to the assessment of “relatedness” in the context of investigational anticancer therapy). It should be noted that although the cycle length is 28 days, cycle duration may extend beyond 28 days in the setting of AEs, which are detailed in Section 7.5.5.

Definition of Maximum Tolerated Dose

The MTD is defined as the dose preceding the dose level at which 2 or more patients experience a DLT during treatment Cycle 1.

The MTD (or a lower dose with a potentially more favorable risk/benefit profile [if identifiable during Stage 1]) will be used in Stage 2 of the study.

Stage 2: Expansion:

During Stage 2, up to 20 additional patients with evidence of MRD as determined locally will be treated at the MTD or maximum tested dose at which multiple DLTs are not observed (identified in Stage 1) so that up to 15 patients with evidence of MRD as determined centrally are evaluable for safety and response at this dose. For inclusion in the study, all patients treated in the expansion phase should have MRD in bone marrow, as determined locally, via at least one of the following modalities: multi-parametric flow cytometry, cytogenetic evaluation, fluorescence *in situ* hybridization (FISH), real-time polymerase chain reaction (PCR), or next-generation gene sequencing. It is anticipated that at approximately 50% of patients evaluated with AML in 1st remission (CR or CRi) will have evidence of MRD.

Tumor Assessments During Stages 1 and 2:

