6.2.1.1 Definition of Dose-limiting Toxicity

During Stage 1, DLT is defined as any of the following occurring during the first cycle of therapy:

- Any treatment-emergent Grade 4 transaminase or CPK elevation (confirmed within 24 hours of initial identification), regardless of duration or relationship to SL-401.
- Any treatment-emergent Grade 4 hematologic toxicity (unrelated to recurrent leukemia or prior AML therapy) lasting > 28 days after the last infusion of SL-401.
- Any treatment-emergent Grade ≥ 3 non-hematologic toxicity (unrelated to recurrent leukemia), with the exception of Grade 3 laboratory toxicities that resolve to Grade ≤ 1 or baseline ≤ 28 days after the last infusion of SL-401, or the following Grade 3 toxicities if they resolve to Grade ≤ 1 or baseline ≤ 21 days after the last infusion of SL-401: arthralgia, myalgia, fever responding to treatment, nausea and/or vomiting (excluding cases that require tube feeding, total parenteral nutrition, or hospitalization) or diarrhea associated with suboptimal prophylaxis or treatment.

SL-401-related toxicities are AEs that are considered by the Investigator to be either possibly, probably or definitely related to investigational SL-401 (Please refer to Section 10.6 for more thorough guidance as to the assessment of “relatedness” in the context of investigational anticancer therapy). It should be noted that although the cycle length is 28 days, cycle duration may extend beyond 28 days in the setting of AEs; see Section 7.5.5. Specific, reversible AEs resulting in a prolongation of cycle 1 to 35 days will not necessitate a dose-reduction for subsequent cycles; these are detailed in Section 7.5.5.

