11.4 Analyses of Safety Data

Safety assessments include DLTs, AEs, SAEs, physical examinations, vital sign measurements, ECGs, clinical laboratory evaluations, and reasons for treatment discontinuation due to toxicity.

Treatment-emergent AEs through 30 days after last SL-401 infusion will be summarized by Medical Dictionary for Regulatory Activities (MedDRATM), Version 13.1 (or higher), system organ class and preferred term. The incidences and percentages of patients experiencing each AE preferred term will be summarized with descriptive statistics. AEs will also be summarized by NCI-CTCAE, Version 4.03 (or higher), grade and by causality (relationship to study drug). Dose-limiting toxicities, Grade 3-4 AEs, SAEs, and AEs resulting in dose modification or treatment discontinuation will also be summarized by preferred term.

Laboratory results will be classified according to NCI-CTCAE, Version 4.03. Laboratory results not corresponding to an NCI-CTCAE term will not be graded. Incidences of laboratory abnormalities will be summarized with descriptive statistics.

Vital signs, physical examination results, and ECGs will be summarized with descriptive statistics.

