1.2.5.2. Safety Parameters

Safety evaluations performed during the study included physical examinations, Eastern Cooperative Oncology Group (ECOG) performance status, measurement of vital signs, 12-lead electrocardiograms (ECGs), clinical laboratory evaluations (hematology, serum chemistry, coagulation, and urinalysis), and monitoring of adverse events (AE) (including treatment serious AEs [SAEs]), DLTs, and concomitant medications (CM).

Further details on the definitions and analysis methods for safety endpoints are provided in [Section 4.4](#).

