4.4.2. Adverse Events

All AEs will be coded using the MedDRA coding system and displayed in tables and data listings using system organ class (SOC) and preferred term (PT).

Analyses of AEs will be performed for those events that are considered treatment-emergent, where treatment-emergent is defined per protocol as any AE with onset after the first administration of Tagraxofusp through 30 days after the last dose of Tagraxofusp, or any event that was present at baseline but worsened in intensity or was subsequently considered drug-related by the Investigator through 30 days after the last dose of Tagraxofusp.

The number and percentage of patients with any treatment-emergent AE (TEAE), with any TEAE assessed by the Investigator as related to treatment, with any TEAE with severity \geq Common Terminology Criteria for Adverse Events (CTCAE) Grade 3, with any SAE, with any AE leading to discontinuation of study treatment, and with any AE leading to dose modification will be summarized by dose group and overall. In these tabulations, each patient will contribute only once (ie, the most related occurrence or the most intense occurrence) to each of the incidence rates in the descriptive analysis, regardless of the number of episodes.

Treatment-emergent AEs summarized by patient incidence rates are not tabulated by severity or relationship to study treatment; therefore, in such tabulations, a patient contributes only once to the count for a given AE SOC or PT. For tabulations that include classification by relationship to study treatment, AEs with missing relationship will be considered related to study drug.

Adverse events of special interest (AESI's) will be determined using MedDRA version 19.0 standardized medical queries (SMQs), high-level terms, or PTs, as follows:

- Possible hypersensitivity events, based on the SMQ Hypersensitivity (broad search).
- Vascular capillary leak syndrome (CLS), based on the MedDRA SMQ [to be provided] in addition to PTs of hypoalbuminaemia, blood albumin decreased, and proteinuria.
- Possible drug-induced liver injury events, based on the SMQ drug-related hepatic disorders (broad search).

Summary tables of AESIs produced will report AESIs as follows:

- AESIs overall and by PT,
- AESIs by PT overall and by grouped cycle (Cycle 1, Cycles 2-4, Cycles \geq 5),
- \geq 3 Grade AESIs overall and by PT,
- Serious AESIs overall and by PT,
- AESIs resulting in drug interruption overall and by PT,

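### The SAP's only DLT definition allows 28 days, not the supplied protocol's 21, for five groups of excepted Grade 3 toxicities, and the SAP plans no DLT summary: a minor reporting inconsistency

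*SAP*

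**What the plan says.** Protocol 6.2.1.1 counts non-hematologic toxicity of Grade 3 or worse in Cycle 1 as dose-limiting, with two exceptions that carry different time limits. The first covers "Grade 3 laboratory toxicities that resolve to Grade ≤ 1 or baseline ≤ 28 days after the last infusion of SL-401". The second covers the "following Grade 3 toxicities if they resolve to Grade ≤ 1 or baseline ≤ 21 days after the last infusion of SL-401", and names arthralgia, myalgia, fever that responds to treatment, nausea or vomiting, and diarrhea linked to inadequate prophylaxis or treatment. The protocol synopsis gives the same two limits.

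SAP 1.2.1 repeats the definition. The laboratory exception keeps 28 days, but the clinical exception now covers the "following Grade 3 toxicities if they resolve to Grade ≤ 1 or baseline ≤ 28 days after last infusion of Tagraxofusp".

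On output, protocol 11.4 states: "Dose-limiting toxicities, Grade 3-4 AEs, SAEs, and AEs resulting in dose modification or treatment discontinuation will also be summarized by preferred term". SAP 1.2.5.2 lists DLTs among the safety parameters and adds: "Further details on the definitions and analysis methods for safety endpoints are provided in" Section 4.4. That section has no DLT definition, derivation, table or listing. The sentence in SAP 4.4.2 that sets out the AE overview runs through treatment-emergent, related, Grade 3 or worse, serious and discontinuation events, and ends with patients "with any AE leading to dose modification will be summarized by dose group and overall". DLTs are not among them. SAP Section 5 reports no departures from the protocol's analyses.

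**The concern.** DLTs carry the primary objective: the MTD, or the highest tested dose without multiple DLTs, is read from them. SAP 1.1.3 says its analyses are the basis for the results sections of the study report. A programmer who needs a DLT definition will find only the one in 1.2.1, and its clinical window is a week longer than the protocol's. If DLT status were derived from that text, some events that the protocol counts would lose the label, and nothing in the SAP would alert the reader.

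The missing DLT summary is a separate gap. It needs closing whichever window proves correct.

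**Working it through.** The plan gives no figure to reproduce here; the check is a comparison of texts followed by short arithmetic.

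**Texts side by side (days from last infusion to resolution)**

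| Place | Grade 3 laboratory | Five named clinical groups |
|---|---|---|
| Protocol synopsis | ≤ 28 | ≤ 21 |
| Protocol 6.2.1.1 | ≤ 28 | ≤ 21 |
| SAP 1.2.1 | ≤ 28 | ≤ 28 |

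**Band of disagreement.** 28 − 21 = 7 days, that is, resolution on days 22 to 28 after the last infusion. In study days, with the last Cycle 1 infusion on day L, the protocol limit is L + 21 and the SAP limit is L + 28.

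- L = 5 (five consecutive days): limits are Day 26 and Day 33; the rules disagree on Days 27–33.
- L = 10 (latest day that protocol 7.5.2 allows): limits are Day 31 and Day 38; the rules disagree on Days 32–38.

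**Direction.** Any event resolved by day 21 is also resolved by day 28. Every event exempt under the protocol is therefore exempt under the SAP, and SAP DLTs are a subset of protocol DLTs.

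**Likely size.** Neither document gives a rate for listed Grade 3 events resolving in the band. Protocol 3.6.1 gives partial context from 92 patients in the earlier study: Grade 3 or worse fever attributed to SL-401 in 1.1%, and nausea in 0%. SAP 3.1 gives 18 Stage 1 patients, so 0.011 × 18 ≈ 0.2 expected fever events, before requiring resolution in a particular week. This is only a rough guide. That study gave a single cycle of product from an earlier process at several doses. It reports attributed events only, whereas this DLT bullet excludes only events due to recurrent leukemia. It gives no Grade 3 rate for arthralgia, myalgia, vomiting or diarrhea.

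**A bound, if 21 days governed Stage 1 and was followed.** Passing 7 and 9 µg/kg/day required at most one DLT patient at each level, and identifying 12 µg/kg/day as a dose without multiple DLTs implies at most one there. At most 3 × 1 = 3 patients at these levels could lose a DLT label. Each change would take a level from 1 to 0, which leaves the escalation result the same. A level above 12 µg/kg/day, if one was opened, is outside this bound; SAP 1.2.1 describes only the three.

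**The case against.** The strongest reply is that SAP 1.2.1 is background. It stands in the part of the SAP headed Information From the Study Protocol and is written in the past tense. The operative rule is protocol 6.2.1.1, and escalation decisions belonged to the safety review committee. Because the SAP specifies no DLT output, the wrong number has no table to feed. Any affected event would still appear among the Grade 3 or worse treatment-emergent events and in the listings; only its DLT label could differ.

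A second reply concerns versions. SAP 1.1.2 takes its objectives from Amendment 5 and SAP Section 7 its flow charts from Amendments 8 and 9. The documents do not show which amendment was in force during Stage 1, so 28 days may be what then applied.

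Both replies stand as limits, and together they make the point minor. They do not remove it. The SAP and the supplied protocol disagree on the definition of the event behind the primary objective, the SAP is silent about it, and the protocol requires a DLT summary that the SAP does not plan. When that summary is produced, the SAP offers the programmer only the 28-day text.

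A reader might infer that the looser window let the trial escalate too far, or that the Stage 2 dose is in doubt. The documents do not support this: SAP 1.2.1 describes an escalation already made and records 12 µg/kg/day as already identified. A reader might also infer that the definition was relaxed on purpose. Nothing shows that; a slip from the adjacent 28-day laboratory clause would explain it equally well, though that too is unproven. Nor does the window alone make Section 5 untrue, since that section speaks of statistical analyses. The missing DLT summary falls more plainly within it.

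**Conclusion.** The inconsistency is real and minor. SAP 1.2.1 gives 28 days where the supplied protocol gives 21, for five groups of Grade 3 toxicities, and SAP 4.4.2 omits the required DLT summary. The effect is confined to DLT labelling and reporting in the study report. Its direction is certain: the SAP count is at or below the protocol count. Its size is unknown, probably few patients or none among 18. The escalation decisions and the 12 µg/kg/day dose are unaffected.

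The under-count assumes that 21 days governed Stage 1 and that reported DLT status is derived from the SAP text; neither can be confirmed from the documents. If 28 days governed, the SAP count is right and what remains is an unexplained difference from the supplied protocol. The missing summary rests on neither assumption.

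**What to change.** 1. Establish which amendment governed Stage 1. If its window was 21 days, as in the supplied protocol, restore 21 days for the clinical exceptions in SAP 1.2.1. If an earlier amendment used 28 days, say so in the SAP and name the amendment.
2. Add to SAP 4.4.2 a Stage 1 DLT table and listing by dose level and preferred term. Base them on the determinations made under the rule used for escalation, without a fresh derivation from SAP 1.2.1.
3. In the listing, flag any patient whose DLT status differs between the two windows, so that the reader can see whether the difference touched anyone.

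The cost is one version check, one number or one sentence in the SAP, and one table and listing covering 18 patients. No new data are needed.
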